#### 5.4 End of Treatment and Safety Follow-Up

As an endpoint driven study, subjects will be on study treatment until approximately 582 study primary endpoints have occurred and have been adjudicated. Participating sites will be informed when the study has reached approximately 582 study primary endpoints and will be asked to schedule the end of study treatment visit for their subjects. The end of study visit must be scheduled within a month of being notified when possible.

Patients still taking study medication at the end of treatment visit will also have a safety follow-up phone call 14 days (+1 week window if needed) after the end of treatment visit. The safety follow-up may be conducted via telephone unless the investigator considers a visit necessary because of ongoing adverse events for which he/she would like to obtain a follow-up measurement.

### 5.5 Assessments and Procedures for Subjects Who Prematurely Discontinue Study medication

For subjects who prematurely discontinue study medication but wish to remain in the trial, they will continue being followed as per the planned study assessments and procedures.

For subjects who prematurely discontinue study medication and also refuse further study visits and procedures, every effort should be made to retain the subjects in the study to obtain information by phone on the occurrence of endpoint events.

For subjects who refuse further study medication, procedures, or phone contact, an end of treatment visit should be performed if possible. For these patients the investigator should make every effort to obtain information on whether or not the subject is alive or dead at the end of the study. If these patients are unable to be reached, this information may be obtained through publicly available sources and/or as permitted by local regulations. If locally allowed, a third party may be used to locate alternative subject contact information and/or vital status in the public domain. That information will be provided to the investigator.

### 5.6 Assessments and Procedures at Occurrence of Efficacy Endpoints

Occurrence of study endpoints, from randomization to trial completion, must be reported to the sponsor within 24 hours of the site’s notification that the study endpoint has occurred. As endpoints will be adjudicated by an independent Clinical Endpoint Committee (CEC), endpoint classification forms will be provided as part of the eCRF. The investigator will record the event on these electronic forms and forward the supporting documentation (hospital admission and discharge note, autopsy reports, ECGs etc.) in a timely manner. These data will be provided to the CEC for adjudication of the event. The CEC consists of the chairman and additional qualified members. Procedures and processes for the CEC will be detailed in the CEC charter.

Table 1 Schedule of Assessments

Subjects who will be in the study for more than 3 years will continue to visit the clinic every 6 months and have the same assessments performed as during the second and third year.

	V1 Screening	V2 Day 0 (randomization)	V3 1M	V4 3M phone	V5 6M	V6 12M	V7 18M	V8 24M	V9 30M	V10 36M	End of Study	Phone 14 days after end of study
Visit windows (weeks)			± 1	± 3	± 3	± 3	± 4	± 4	± 4	± 4		+ 1

Informed Consent for Study Protocol	X											
ACDY9 genetic determinant (blood draw)	X											
Assessment of eligibility	X	X										
Demographic Information	X											
Query subjects for new/changes in contact information		X			X		X		X			
Pregnancy Test (local)		X										
Physical Exam and Medical History		X									X	
Blood Pressure, Pulse, Weight		X	X		X	X	X	X	X	X	X	
Height		X										
Blood draw for serum creatinine, HbA1c, fasting lipids and hsCRP (central lab)		X			X							
Informed consent for optional genetic and biomarker evaluations		X										
Blood draw for optional genetic and biomarker evaluations		X			X							
Prev/Conc Med		X	X	X	X	X	X	X	X	X	X	
Adverse Events			X	X	X	X	X	X	X	X	X	X
Dispense Study medication		X			X	X	X	X	X	X		
Return unused Study medication					X	X	X	X	X	X	X	

\*Optional phone calls by the site to the patient may be conducted between 6 month visit intervals

\*\* Procedures that require physical contact with patients such as obtaining, blood pressure, pulse, weight, and an End of Study physical exam are to be performed whenever possible, but may be considered as optional in situations where direct physical contact with the patient is not locally allowed or determined to be hazardous to the patient and/or staff due to the COVID-19 pandemic.

## 5.7 Efficacy Assessments and Procedures

Efficacy assessments of this study are listed below. A detailed description of the analysis of these parameters is included in Section 8, ‘Statistical Considerations and Analytical Plan’.

All primary and secondary endpoint events will be adjudicated by the CEC.

### 5.7.1 Primary Efficacy Assessment

The primary efficacy assessment in this trial is the time to the first occurrence of any component of the composite endpoint of:

- Cardiovascular (CV) death
- Resuscitated cardiac arrest
- Non-fatal MI
- Non-fatal stroke

A detailed description of criteria for classification of endpoints is documented in the CEC charter. The charter will also include information on supporting documents to be provided,

data flow and meeting schedule of the CEC. Study sites will be given a list of the documents that they will need to provide when an endpoint is suspected.

### 5.7.2 Secondary Efficacy Assessments

The key secondary efficacy assessments in this trial are the time to the first occurrence of:

- The composite of CV death, resuscitated cardiac arrest, non-fatal MI, non-fatal stroke, or hospitalization for ACS (with ECG abnormalities) requiring coronary revascularization
- The composite of CV death, resuscitated cardiac arrest, non-fatal MI, non-fatal stroke, hospitalization for ACS (with ECG abnormalities), or unanticipated coronary revascularization
- The composite of all cause death, resuscitated cardiac arrest, non-fatal MI, or non-fatal stroke

Other secondary efficacy assessments are listed below.

Time to first occurrence of:

- The composite of CV death, resuscitated cardiac arrest, non-fatal MI, non-fatal stroke, or hospitalization for new or worsening heart failure
- The composite of CV death, resuscitated cardiac arrest, non-fatal MI, non-fatal stroke, hospitalization for ACS (with ECG abnormalities) requiring coronary revascularization, or hospitalization for new or worsening heart failure
- The composite of all-cause death, resuscitated cardiac arrest, non-fatal MI, non-fatal stroke, or hospitalization for new or worsening heart failure
- Fatal or non-fatal MI
- All-cause death

### 5.7.3 Exploratory Assessments

Blood draw for serum creatinine, fasting lipids, hsCRP, and HbA1c will be obtained according to the schedule summarized in Table 1 and analyzed by the central laboratory. Exploratory laboratory assessments are change from baseline in levels of lipids as well as the change in hsCRP. Healthcare resource utilization information will also be collected.

Patients who volunteer for the optional biomarker sub-study will have additional blood samples collected at Visits 2 and 5 for future genetic and non-genetic analyses. Protection

of subject confidentiality will extend to any data generated from the assaying of these samples. These samples will be frozen and kept for future use to evaluate biomarkers related to cardiovascular disease and the response to treatment.

A laboratory manual providing instructions for the collection and handling of blood samples will be provided.

## 5.8 Safety Assessments and Procedures

### 5.8.1 Adverse Events

Adverse events will be collected throughout the study after randomization. At each visit starting at V3, the investigator will ask the subject if any untoward medical event occurred since the last visit. For each event, the date of onset and end, intensity, relationship to study medication, and outcome will be recorded on the eCRF.

### 5.8.2 Vital signs

Seated blood pressure and pulse will be recorded after at least a 5-minute rest. Vital sign checks will be performed according to the schedule summarized in Table 1.

### 5.8.3 Physical examination and medical history

Physical examinations will include examination of the following body systems: general appearance, chest/lungs, and cardiovascular. All clinically significant changes from randomization to trial completion should be reported as an AE in the source data and the eCRF. Medical history will consist of detailed information regarding the index ACS event, and risk factors for cardiovascular disease.

### 5.8.4 Laboratory Assessments

Blood samples are to be collected at Visit 1 (screening), Visit 2 (Day 0) and Visit 5 (Month 6). Blood samples at Visits 2 and 5 are ideally to be collected in the fasting state (minimum of 10 hours without food; subjects are allowed to drink water, but no coffee or tea). The procedures for the collection, handling, storage and shipping of laboratory samples are specified in a separate laboratory manual.

#### 5.8.4.1 Serum Creatinine and HbA1c

Blood draw for serum creatinine and HbA1c will be obtained according to the schedule summarized in Table 1 and analyzed by the central laboratory. All clinically significant changes from randomization to trial completion should be reported as an AE in the source data and the eCRF.

#### 5.8.4.2 Pregnancy Test

$\beta$ -HCG levels test will be obtained and analyzed locally in all women of childbearing potential prior to randomization (Table 1).

## 6. INVESTIGATIONAL MEDICINAL PRODUCT

### 6.1 Dose and Schedule of Study medication and Placebo

DalCor (sponsor) will supply dalcetrapib 300mg film-coated tablets and matching placebo tablets to investigators. Subjects will take 600 mg of dalcetrapib or placebo (2 tablets) once daily. Study medication should be taken with food, preferably with the largest meal of the day. Subjects should be encouraged to take the medication at approximately the same time each day.

Subjects who take study medication with breakfast should be instructed not to take study medication at home in the morning of V2 and V5 (fasting blood samples are preferred) but to wait until after collection of blood at the clinic.

#### 6.1.1 Dose Modifications and Delays

In the event of a subject forgetting to take drug with their largest meal that day, they can take the study drug later in the day and return to their regular schedule the next day. In the event of a subject not taking drug on a given day, he or she should not take more than the daily dose on the following day.

Temporary interruptions of study medication are allowed. Interruptions of study medication for longer than 14 days need approval of the sponsor whenever possible. In the event of a subject experiencing intolerable adverse events considered related to study medication by the investigator, the investigator should consider decreasing the dose to one tablet once daily before interrupting or permanently discontinuing study medication.

### 6.2 Formulation, Packaging and Labeling

Dalcetrapib will be provided as film-coated tablets of 300 mg. Tablets are white and capsule-shaped, identical in appearance to placebo tablets.

The study medication must be stored in a locked, secured, temperature controlled location of up to 25° C. A daily temperature log must be maintained by the site. Any temperatures exceeding 25° C should be reported to the Sponsor/designee immediately along with the following information: the minimum and maximum temperature of the excursion, duration in hours, and the medication kit numbers involved. The drug should be immediately placed at the proper temperature and quarantined (not dispensed to subjects) until notification from the Sponsor is received that the drug is acceptable to use or must be destroyed/returned.

Likewise, subjects should be informed that study medication must be stored at 25° C or below.

Subjects will take their daily dose of dalcetrapib or placebo as shown below.

Dose Group	No. of Tablets	
	300 mg dalcetrapib tablet	Placebo
600 mg of dalcetrapib	2	0
Placebo	0	2

Please note that placebo tablets contain lactose (435 mg/tablet) and may lead to problems in subjects with severe lactose intolerance.

Each site will receive a supply of individually labeled double-blind study medication kits. Each kit will be labeled with a label including dosing instructions, the visit number and the subject number to be added by site personnel.

### 6.3 Randomization

Subjects will be randomized to dalcetrapib 600 mg or placebo in a 1:1 ratio stratified by region and ACS index event (MI or hospitalization for ACS [ECG Abnormalities without Biomarkers], see sections 4.1.1 and 4.1.2), according to a computer-generated global randomization code. The subject randomization numbers will be allocated sequentially in the order in which the subjects are enrolled. Investigators are to use the IWRS to obtain randomization numbers for subjects they randomize in the study.

The Master Randomization List will be kept in a central repository at the Coordinating Center with access to the unblinded statistician only. No open key to the code will be available at the study center, to the monitors of the Contract Research Organization (CRO), project statisticians, or to the project team.

### 6.4 Blinding and Unblinding

The blind during the study is maintained by administration of placebo tablets to subjects in the placebo group. The Randomization List will not be available at the study center, to the Project Manager and monitors of the contract research organization(s) CRO(s), project statisticians or to the project team. If the identification of the test medication is necessary for subject management (in the case of serious adverse event) the investigator will be able to break the code by contacting the IWRS provider. A note to file should be written which will be archived with other study documents. Treatment codes should not be broken except in the case of emergency situations. If the investigator wishes to know the identity of the treatment given to study subjects for any other purpose, this request should first be discussed with the DalCor Chief Medical Officer.

Unblinding for ongoing safety monitoring by the DSMB will be performed according to adequate procedures in place to ensure integrity of the data as outlined in a separate DSMB charter.

All other individuals directly involved in this study will remain blinded until the final analysis of the primary parameter.

## 6.5 Assessment of Compliance

Accountability and subject compliance will be assessed by maintaining adequate drug dispensing and return records.

Subjects will be asked to return all used and unused drug supply containers at each visit as a measure of compliance.

A Drug Dispensing Log must be kept current and should contain the following information:

- the identification of the subject to whom the study medication was dispensed
- the date[s] and quantity of the study medication dispensed to the subject
- the date[s] and quantity of the study medication returned by the subject

This inventory must be available for inspection by the Monitor. The dispensing logs must be returned to DalCor or DalCor designee at the end of the study.

## 6.6 Destruction of Study Medication

Each site will be instructed by their monitor on the details of drug return/destruction for their site.

# 7. SAFETY INSTRUCTIONS AND GUIDANCE

## 7.1 Adverse Events (AEs) and Laboratory Abnormalities

### 7.1.1 Clinical AEs

Per the International Conference of Harmonization [ICH], an AE is any untoward medical occurrence in a subject or clinical investigation subject administered a pharmaceutical product and which does not necessarily have a causal relationship with this treatment. An AE can therefore be any unfavorable and unintended sign [including an abnormal laboratory finding], symptom, or disease temporally associated with the use of a medicinal [investigational] product, whether or not considered related to the medicinal [investigational] product. Pre-existing conditions which worsen during a study are to be reported as AEs.

#### 7.1.1.1 Intensity

All clinical AEs encountered during the clinical study will be reported on the AE page of the eCRF. Intensity of AEs will be graded on a four-point scale [mild, moderate, severe, life-threatening] and reported in detail on the eCRF.

Mild	discomfort noticed but no disruption of normal daily activity.
Moderate	discomfort sufficient to reduce or affect daily activity.
Severe	inability to work or perform normal daily activity
Life-Threatening	represents an immediate threat to life

#### 7.1.1.2 Drug - Adverse Event Relationship

Relationship of the AE to the treatment should always be assessed by the investigator as either Related or Not Related . The following criteria should be considered in order to assess the relationship:

- reasonable temporal association with administration of the study drug
- existence of alternative causes that could on their own have caused the reaction, like the subject's medical condition
- known pattern of response to the suspected drug
- de- and rechallenge information

#### 7.1.1.3 Serious Adverse Events

A Serious Adverse Event (SAE) is any AE that at any dose fulfills at least one of the following criteria:

- is fatal; [results in death; NOTE: death is an outcome, not an event]
- is life-threatening [NOTE: the term "Life-Threatening" refers to an event in which the subject was at immediate risk of death at the time of the event; it does not refer to an event which could hypothetically have caused a death had it been more severe].
- required in-patient hospitalization or prolongation of existing hospitalization\*;
- results in persistent or significant disability/incapacity;
- is a congenital anomaly/birth defect;
- is medically significant or requires intervention to prevent one or other of the outcomes listed above.

*\* NOTE: Any hospital admission with at least one overnight stay will be considered an inpatient hospitalization. An emergency room visit without hospital admission will not be recorded as a serious adverse event (SAE) under this criterion, nor will hospitalization for a procedure scheduled or planned before signing of informed consent. However, unexpected complications and/or prolongation of hospitalization that occur during elective surgery should be recorded as AEs and assessed for seriousness.*

*Admission to the hospital for social or situational reasons (i.e., no place to stay, live too far away to come for hospital visits) will not be considered inpatient hospitalizations.*

The study will adhere to the full requirements of the ICH Guideline for Clinical Safety Data Management, Definitions and Standards for Expedited Reporting, Topic E2 and comply with local regulatory requirements (see Appendix 2).

#### 7.1.1.4 Project-Specific Definition of SAEs

In this trial, positively adjudicated endpoints by the CEC (irrespective of investigators' causality) as well as those negatively adjudicated by the CEC and reported as unrelated to study medication by the investigators will be exempted from SAE reporting. However, all other events meeting SAE criteria will be reported as SAEs to the Sponsor.

Thus, the following events will not be reported as SAEs unless negatively adjudicated and considered study medication related by the investigator:

- Cardiovascular (CV) death
- Resuscitated cardiac arrest
- Non-fatal MI
- Non-fatal stroke
- Hospitalization with ACS (with ECG abnormalities)
- Hospitalization for ACS (with ECG abnormalities) requiring coronary revascularization
- Unanticipated coronary revascularization
- Hospitalization for new or worsening heart failure
- All-cause death

These events will be reported on the appropriate eCRF pages for the collection of information on endpoint events and forwarded to the CEC.

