### 7.2 Handling of Safety Parameters

#### 7.2.1 Reporting of AEs

All new adverse events occurring during the study should be recorded on the AE page of the eCRF. Adverse events that occur intermittently should be recorded as one AE. Adverse events should be collected and reported from randomization to trial completion.

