#### 7.2.2 Reporting of Serious Adverse Events

Any clinical AE or abnormal laboratory test value that is serious [as defined in section 7.1.1.3 above] and which occurs during the course of the study must be reported to the sponsor within 24 hours of the investigator becoming aware of the event.

Related Serious Adverse Events MUST be collected and reported regardless of the time elapsed from the last study medication administration, even if the study has been closed.

Like AEs in general, unrelated Serious Adverse Events must be collected and reported during the study and to trial completion.

The definition and reporting requirements of ICH Guideline for Clinical Safety Data Management, Definitions and Standards for Expedited Reporting, Topic E2 will be adhered to. Complete information can be found in Appendix 2.

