A serious adverse event occurring during the study or which comes to the attention of the investigator within 14 days during the protocol-defined follow-up period after stopping the treatment or during the protocol-defined follow-up period, if this is longer, whether considered treatment-related or not, must be reported. In addition, a serious adverse event that occurs after this time, should also be reported if considered related to test “drug”.

Such preliminary reports will be followed by detailed descriptions later which will include copies of hospital case reports, autopsy reports and other documents when requested and applicable.

For serious adverse events, the following must be assessed and recorded on the AEs page of the eCRF: intensity, relationship to test substance, action taken, and outcome to date.

The investigator must notify the Ethics Committee/Institutional Review Board of a serious adverse event in writing as soon as is practical and in accordance with international and local laws and regulations.

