6.4.1.1 Evaluation of Primary Endpoint Adjudication

In order to evaluate the consistency of subject outcomes as assessed by the investigator and as adjudicated by the CEC, the concordance between both assessments for the components of the primary endpoint will be summarized using descriptive statistics.

In addition, to go into more depth for death, types of death (CV, non-CV, undetermined), as reported by the investigator and as adjudicated by the CEC, will be summarized using descriptive statistics. No formal statistical testing will be done.

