6.5.2.2 Serious Adverse Events

SAEs will be summarized similarly to all TEAEs and presented in a subject data listing.

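### Suspected non-fatal endpoints that the CEC rejects and the investigator calls unrelated are exempt from SAE reporting, and no by-arm safety output is specified for them

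*Protocol*

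**What the plan says.** Protocol 7.1.1.4 removes two groups from SAE reporting. The first is endpoints that the CEC confirms. The second is suspected endpoints "negatively adjudicated by the CEC and reported as unrelated to study medication by the investigators will be exempted from SAE reporting". It then lists the event types concerned (primary components, ACS hospitalization, revascularization, heart-failure hospitalization, deaths) and gives a single way back: "the following events will not be reported as SAEs unless negatively adjudicated and considered study medication related by the investigator". On where the data go, it says: "These events will be reported on the appropriate eCRF pages for the collection of information on endpoint events and forwarded to the CEC".

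Other passages point the other way or leave the matter open:

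- Protocol 7.2.1 has no carve-out for endpoint events: "All new adverse events occurring during the study should be recorded on the AE page of the eCRF". Protocol 7.1.1.1 says much the same for clinical AEs.
- Protocol 7.2.2 defines seriousness by reference to 7.1.1.3, not 7.1.1.4, and says that "unrelated Serious Adverse Events must be collected and reported during the study and to trial completion".
- Protocol Appendix 2 says that SAEs in the study or follow-up period, "whether considered treatment-related or not, must be reported".
- SAP 5.2 gives the generic seriousness criteria and does not repeat the exemption.

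On analysis, SAP 6.5.2.2 says only that "SAEs will be summarized similarly to all TEAEs and presented in a subject data listing". SAP 6.4.1.1 compares investigator and CEC assessments: "the concordance between both assessments for the components of the primary endpoint will be summarized using descriptive statistics". It adds a summary of types of death. It does not say that either summary is split by arm.

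**The concern.** Exempting confirmed endpoints is workable, because they are counted and compared in the efficacy analysis. The second exemption has no such counterpart. A subject may be admitted with suspected heart failure, the CEC may decide that it was something else, and the investigator may rate it unrelated. That admission is then not an endpoint and, under 7.1.1.4, not a reported SAE, even if it meets the seriousness criteria.

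A by-arm SAE comparison exists partly to show imbalances that case-by-case causality judgments cannot see. Here the causality judgment is applied first and decides which rejected events enter the comparison. Long-term safety is a stated objective (Protocol 2.2), Protocol 8.1.3 rests safety on AEs and vital signs, and central-laboratory samples after randomization are taken only at month 6. The SAE table therefore carries much of the long-term safety evidence.

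**Working it through.** No arithmetic decides this point. The one design figure nearby is 582 events (Protocol 8.2.1: 22% risk reduction, two-sided alpha 0.05, 85% power, 1:1 allocation). It reproduces: 4 × (1.960 + 1.036)² / (ln 0.78)² = 35.91 / 0.0617 = 582. Nothing below depends on it. The check is to follow a non-fatal suspected endpoint through the documents.

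**Step 1. Status under Protocol 7.1.1.4 and SAP 4.1–4.2**

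| CEC decision | Investigator causality | Counted as endpoint | Reported as SAE |
|---|---|---|---|
| Confirmed | either | yes | no |
| Rejected | related | no | yes |
| Rejected | unrelated | no | no |

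The second and third rows differ only in the causality rating. The third row is the gap.

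**Step 2. Does a SAP output recover the third row?**

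- SAE summary (SAP 6.5.2.2): no rule adds rejected referrals.
- Treatment-emergent AE tables (SAP 6.5.2.1): possible, if the site also completed the AE page as Protocol 7.1.1.1 and 7.2.1 require. Protocol 7.1.1.4 requires the endpoint page and neither demands nor excludes the AE page. Even then, the event appears as an AE, not as a rejected referral.
- Concordance summary (SAP 6.4.1.1): covers primary components only, descriptively, with no by-arm split stated. Rejected ACS, revascularization and heart-failure referrals are outside it.
- Deaths (SAP 6.5.2.4 listing, SAP 6.4.1.1 types of death): fatal cases remain visible, so the point is limited to non-fatal events.

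**Step 3. Do the rules agree?**

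| Passage | Rejected, unrelated, serious event |
|---|---|
| Protocol 7.1.1.4 | not reported as an SAE |
| Protocol 7.2.2 | reported as an SAE |
| Protocol Appendix 2 | reported as an SAE |
| SAP 5.2 | meets the SAE definition |

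A site following the first row and a programmer following the last would expect different contents in the SAE table. The SAP says that it supersedes the protocol where they differ, but it cannot tabulate an event that was never entered as an AE or SAE.

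**Step 4. Timing.** Protocol 7.2.2 requires an SAE report within 24 hours. Under 7.1.1.4 a suspected endpoint rated as drug-related becomes reportable as an SAE only after the CEC rejects it. Protocol 5.6 does give the sponsor notice of the endpoint within 24 hours, so the event is known. What is unstated is when the SAE report itself falls due.

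**The case against.** The strongest reply is that 7.1.1.4 exempts events from SAE reporting to the sponsor, not from AE recording. Protocol 7.1.1.1 and 7.2.1 send all AEs to the AE page, and the SAP's own SAE definition would class a recorded hospitalization as serious. Section 7.1.1.4 also keeps SAE reporting for all other serious events, and a rejected referral with a different final diagnosis might be read as one of these. This part stands: a reader might infer that the events appear nowhere in the safety data, and the documents do not show that. They show an omission from SAE reporting by rule, with the AE route left to how each site read the protocol.

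Other stronger readings also fail:

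- A reader might infer that the SAP 6.4.5.3 analysis censoring at COVID-19 SAEs loses admissions filed as suspected endpoints. That section says that sites were asked to report all COVID-19-related SAEs and that the CEC reviewed events for relatedness to COVID-19. A loss is not shown.
- A reader might infer that the DSMB could not see these events. Its data flow is in a separate charter (Protocol 10.2), which is not available here.
- A reader might put a count on the gap. Assuming 10% to 30% of primary-type referrals are rejected alongside 582 confirmed, rejections would number 582 × 0.10/0.90 = 65 to 582 × 0.30/0.70 = 249. If 95% of these were rated unrelated, 61 to 237 would be exempt. Neither rate is in the documents. The 582 are subjects with a first event (SAP 2.1), not referrals. Some referrals are not serious, some are confirmed as another component, and some will be on the AE page. The range also leaves out ACS, revascularization and heart-failure referrals and says nothing about imbalance between arms.

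**Conclusion.** The concern holds in limited form. Under Protocol 7.1.1.4 a non-fatal suspected endpoint that is rejected and rated unrelated is neither a counted endpoint nor a reported SAE, and investigator causality alone separates it from one that is reported. The SAP specifies no by-arm safety output for such events, most clearly for the ACS, revascularization and heart-failure types. The exemption contradicts Protocol 7.2.2 and Appendix 2 and is absent from SAP 5.2.

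The size cannot be derived from the documents, and neither a loss from every table nor a bias between arms is demonstrated. Sample size, power and the primary analysis are unaffected. The conclusion assumes that sites followed 7.1.1.4 as written. To the extent that they also completed the AE page and marked seriousness, the gap is smaller. It is worth correcting because the SAE comparison is otherwise incomplete by rule and the remedy is cheap.

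**What to change.** 1. Reconcile Protocol 7.1.1.4 with 7.2.1, 7.2.2, Appendix 2 and SAP 5.2. State whether suspected endpoints also go on the AE page, and when a suspected endpoint judged drug-related is due as an SAE report.
2. Limit the exemption from the SAE analysis to positively adjudicated endpoints.
3. In SAP 6.5.2.2 add a by-arm table of all investigator-reported suspected endpoints by CEC outcome. Include negatively adjudicated events that meet the SAP 5.2 seriousness criteria in the SAE summary, whatever their causality rating. Code them from the endpoint pages and check them against the AE page so that none is counted twice.

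The third step matters most now. SAP Amendment 3 is dated July 2021 and 6149 subjects are already randomized, so new protocol wording alone would not recover past events. The table uses data already held: the endpoint pages, with the supporting documents that Protocol 5.6 requires sites to forward. It assumes that these are enough to code a diagnosis and judge seriousness. The downside is modest coding and programming work.
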